Annual community-based HIV testing, mobile testing, self-testing and clinic-based testing opportunities are available to people living in Agincourt, South Africa. Despite these ongoing efforts, testing uptake remains low. People with low SES, high levels of HIV stigma, immigrants, men, and those who distrust the allopathic health system are less likely to receive regular HIV testing and more likely to visit a traditional healer. In 2019, 7.97 million South Africans (22.7% of adults) were living with HIV with women bearing a disproportionate burden (26.6% among females vs. 14.8% among males). Though women bear a larger HIV burden, rural South Africa's "hidden HIV population" comprises patients that the allopathic health system fails to reach. In Mpumalanga province, only 33.9% of adults aged 15-59 received an HIV test in the past year. Undiagnosed HIV infection is highest among men, those with low SES, those with high perceived HIV stigma, and those who believe a traditional healer can cure HIV or deny the existence of the disease. Fear of stigma and discrimination, harmful gender norms, confidentiality fears, and a lack of policies supporting these populations render them reluctant to utilize clinic-based testing. We propose to create a new testing option to test those individuals for whom other testing mechanisms fail.

While extremely successful, community-based HIV testing is still refused by 12-20% of the population. In a rigorous systematic review of 117 community-based testing strategies in 16 African countries, index, self, mobile, and door-to-door testing achieved the highest uptake (88%, 87%, 87% and 80%, respectively). While we have eliminated the need for people to travel for their test (e.g. mobile testing), ensured confidentiality (self-testing), and targeted those at high-risk (index testing), South Africa still has a testing and linkage to care gap among difficult to reach subpopulations. People who perceive, experience or internalize stigma or other forms of marginalization are more likely to utilize traditional healers, less likely to seek care at a health facility, and less likely to undergo HIV testing.

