Traditional healers can bridge the testing gap between “non-testers” and the allopathic health system. Traditional healers have been successfully engaged in health systems to promote care linkage among people living with diabetes, TB, HIV, malaria, and mental illness- many of whom initially did not believe in their allopathic diagnosis until a healer convinced them that their condition was not caused by a curse. Those who are hesitant to test need a trusted and culturally concordant provider (traditional healer) to both vouch for and deliver the HIV test, and the same provider to create a bridge to the allopathic health facility, providing a metaphorical “safe space” for the patient while they transition to HIV care. Traditional healers are strongly motivated to play this role for two reasons: (1) Better patient health outcomes are strongly correlated with perceived quality of traditional healer care. Healers do not want to be associated with high levels of morbidity or mortality, as it is bad for business; and (2) Healers are excited at expanding their public health services. As allopathic medical knowledge is disseminated, healer views on disease causation are expanding to include the germ theory of disease. Patients are open to this partnership, given their inclination to ping-pong between the two systems depending on their needs.

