## 5. Methods

## Measurement of Results

*Community member (those offered HIV testing) and healer outcomes:* Participants will complete both a baseline and 7-month post-enrollment questionnaire using the ACASI-system on a tablet. Data collection at 7 months will include the baseline survey and additional questions about uptake of HIV testing outside of the study and feedback about the acceptability and satisfaction with the study experience. These will be conducted by a study assistant based in the Agincourt area who is fluent in English and xi-Tsonga. The number of participants approached, the number who agree to testing and counseling (including testing outcome), and reports on the impact of performing HIV testing and counseling on healer income will be collected by the traditional healer. Health clinic research staff will collect uptake of testing during one of the “Open House” events and during non-open house days (if, for example a patient seeks testing during regular clinic hours). Clinical data will be accessed using “Clinic Link” which allows us to gain access to relevant clinical data, including ART uptake and retention in care. Data from clinical providers who participate in the stigma reduction intervention will complete surveys at study initiation and immediately after the study has concluded.

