Baseline	Enrollment	Demographics, HIV Stigma, Trust in allopathic provider, belief in HIV test, use of traditional medicine, perceived risk of HIV
Baseline	Healer-initiated C&T, including stigma reduction	Attendance, HIV status, enrollment in care and treatment if positive
Month 6	HIV re-test	Attendance, HIV status, enrollment in care and treatment if positive
Month 7	Follow-up survey & qualitative questions	HIV Stigma, Trust in allopathic provider, belief in HIV test, use of traditional medicine, perceived risk of HIV, experience with the healer-clinician collaborative

Table 6: Project Activities and Data Collection Points

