### **Data Analysis**

Given that participants may complete none, one, two, or all three of these intervention components, we will consider four different intervention component variables to the Healer-Clinician HIV Prevention Collaborative intervention: (1) Uptake of healer-initiated HIV counseling and testing (vs. those who did not), (2) Participation in additional counseling sessions (vs. those

who did not), (3) Attendance at  $\geq 1$  Open House event at the health facility (vs. those who did not), and (4) An index ranging from 0 to 3 indicating the number intervention components completed.

The primary outcome among those testing HIV negative or refusing testing is uptake of health facility HIV testing within 6 months. We will operationalize the outcomes in the positive (e.g., tested at health facility within 6 months) such that the risk ratios (RR) for the intervention components will be  $>1.0$  if effective. We will estimate the association of each intervention component individually (numbers 1-3 above) using separate regression models that are each further stratified by potential modifiers such as gender, age, sexuality, immigration status, and other baseline characteristics. We will use *modified Poisson regression* models for each intervention component to estimate risk ratios and 95% confidence intervals.

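### Each self-selected intervention component is analysed in its own model with no adjustment for baseline confounders, so its RR mixes the component's association with who chose it

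*Combined protocol and SAP*

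**What the plan says.** The Data Analysis part of section 7 defines the exposures from what participants take up: "Given that participants may complete none, one, two, or all three of these intervention components". The components are the healer-delivered test, additional counselling, and attendance at one or more Open House events. A fourth variable counts components from 0 to 3. The outcome is facility testing within 6 months among those who test negative or refuse.

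The model statement is "We will estimate the association of each intervention component individually (numbers 1-3 above) using separate regression models". Each model is then stratified by "potential modifiers such as gender, age, sexuality, immigration status, and other baseline characteristics". The estimator is modified Poisson regression with 95% intervals, and an RR above 1.0 is what an effective component is expected to show. No adjustment covariate, weighting method or model holding other components fixed is named, there or elsewhere. The 0-3 index is defined, but no model is described for it.

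Table 6 lists the baseline data as "Demographics, HIV Stigma, Trust in allopathic provider, belief in HIV test, use of traditional medicine, perceived risk of HIV". Section 9 says the study is not randomised, but concludes only that healer testing cannot be compared with other testing modalities. It does not mention self-selection into components.

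**The concern.** Nobody is assigned to a component. The Introduction names traits that go with less testing, including distrust: "those who distrust the allopathic health system are less likely to receive regular HIV testing and more likely to visit a traditional healer". It says people facing stigma or marginalisation are "more likely to utilize traditional healers, less likely to seek care at a health facility, and less likely to undergo HIV testing". A trait that predicts facility testing and also affects who accepts a component confounds that component's RR. Stratifying on one variable controls only that variable.

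This is the only analysis given for the primary outcome in those testing negative or refusing, and section 9 intends the pilot to inform a larger randomised trial. An inert component could look useful, or a useful one could look inert. Covariates chosen after the data are seen would be open to challenge.

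**Working it through.** **1. The plan's own figures.** Table 1 gives power for RR 2.0 with 135 per stratum, 30% baseline testing and component uptake of 40/50/60/70% as 0.924/0.928/0.924/0.850. Simulating an unadjusted modified Poisson test (two-sided 5% assumed; 40,000 runs) gives 0.940/0.940/0.921/0.863. Of the cells tried, 37 of 48 in Table 1 and 17 of 24 in Table 2 agree within 2 points, and the misses are mostly of the size expected from 500 simulations. The tables therefore fit a crude two-group comparison, and nothing in them implies covariates.

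**2. Confounding of an inert component.**
- From section 4: uptake q of 70%, 60% and 50% for the three components.
- Assumed, with no source in the documents: a binary baseline trait held by 50%, its odds ratio (OR) with uptake, and its risk ratio r on testing.
- Let a and b be uptake with and without the trait. Then a + b = 2q, and the OR fixes a.
- Trait prevalence is p1 = a/(2q) in takers and p0 = (1 − a)/(2(1 − q)) in non-takers.
- Crude RR = [1 + p1(r − 1)] / [1 + p0(r − 1)].

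Example with q = 0.5, OR 3, r = 2: a = √3/(1 + √3) = 0.634, so p1 = 0.634 and p0 = 0.366. Crude RR = 1.634/1.366 = 1.20.

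| Trait–uptake OR (or its inverse) | r | Crude RR, trait raises uptake (q = 70/60/50%) | Crude RR, trait lowers uptake |
|---|---|---|---|
| 2 | 1.5 | 1.07/1.07/1.07 | 0.93/0.93/0.93 |
| 2 | 2 | 1.12/1.12/1.12 | 0.89/0.89/0.89 |
| 3 | 2 | 1.20/1.20/1.20 | 0.84/0.84/0.84 |
| 3 | 3 | 1.32/1.32/1.31 | 0.78/0.77/0.76 |
| 5 | 2 | 1.30/1.30/1.29 | 0.79/0.78/0.77 |
| 5 | 3 | 1.50/1.49/1.47 | 0.70/0.69/0.68 |

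**3. What that does to a nominal 5% test.** Take N = 600 × 0.95 = 570, 50% uptake, the trait in 65% of takers and 35% of non-takers, and testing of 40% with the trait and 20% without.
- Takers test at 0.65 × 0.40 + 0.35 × 0.20 = 0.33 and non-takers at 0.27, so the RR is 1.22.
- The SE of log RR is √[0.67/(285 × 0.33) + 0.73/(285 × 0.27)] = 0.129. Then z = 0.201/0.129 = 1.56, and rejection is about 34%.
- With 135 people the SE is 0.129 × √(570/135) = 0.265, z = 0.76, and rejection is about 12%.
- Simulation (400 runs) gave 34% in either direction at 570, and 8% and 16% at 135. In a milder case (60% vs 40%; testing 36% vs 24%) it gave 7 to 8% at 570 and 6% at 135.
- With the trait in the model the RR returned to 0.96–1.00 in the stronger case, with rejection of 3 to 10%. The return towards 1 holds by construction, because the only confounder was measured.

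**4. The other components.** Suppose counselling (60%) is inert, Open House attendance (50%) has RR 2.0, and their uptake has correlation phi.
- P(both) = 0.30 + phi × √(0.6 × 0.4 × 0.5 × 0.5). At phi 0.3 this is 0.373.
- Open House attendance is then 0.622 in counselling takers and 0.316 in others, so counselling alone shows 1.622/1.316 = 1.23. At phi 0.5 it shows 1.704/1.194 = 1.43.
- Adjusting for a baseline trait leaves these values essentially unchanged (1.22 and 1.43 in simulation).

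**5. Whether the data support adjustment.** At 30% overall testing, 600 enrolled give 600 × (0.90 to 0.95) × 0.30 = 162 to 171 events. Nine covariates plus the component make 10 parameters, or 16 to 17 events each. The tables' stratum sizes instead match about 300 enrolled (300 × 0.90/2 = 135; 300 × 0.95 × 0.4 = 114), although the text says 600. With 300 there are 81 to 86 events: 8 to 9 per parameter for the full set, and 16 to 17 for a four-covariate core set plus the component. In a stratum, the tables' RR 2.0, 50% uptake case (45% overall) gives 135 × 0.45 = 61 or 115 × 0.45 = 52 events. That is 15 or 13 for each of four parameters (three core covariates and the component).

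**The case against.** **It is a pilot that speaks of association.** Its stated hypothesis concerns trust and stigma, not these RRs. That limits the severity. But the same paragraph ties an RR above 1.0 to effectiveness, and section 4 wants subgroups that benefit most to be identified.

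**The strong cases have no source.** This stands. The mild cases move the RR by only about 7 to 12%, and at the tables' stratum sizes false rejection rises much less than in a pooled model of 570.

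**The direction is not established.** A reader might infer that distrustful clients accept the healer's test more and facility testing less, so that benefit is masked. The documents do not show this. The Introduction links distrust to visiting a healer, and everyone enrolled is already a healer's client with no test result in the past year. The remark that "Those who are hesitant to test need a trusted and culturally concordant" provider states a need, not an uptake pattern. The opposite inference, that willing people inflate every RR, is equally unproven.

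**Spill-over need not be bias.** A reader might infer that separate models wrongly credit one component with another's effect. If counselling leads people to an Open House, the 1.23 or 1.43 in step 4 is partly a legitimate total effect. The documents do not fix the order of the components, so a joint model is not automatically the right primary analysis.

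**Conclusion.** The concern holds as an omission with a practical remedy. The plan fits unadjusted models to self-selected exposures in a non-randomised study, names plausible confounders in its own Introduction, and largely collects the data needed to adjust for them. The crude RR for an inert component could be 1.07 to 1.12 or 1.20 to 1.50, with 0.89 to 0.93 or 0.68 to 0.84 if the trait lowers uptake. Every one of those figures rests on assumed trait strengths, so they show what is possible and do not estimate the actual bias. The documents support no claim about its actual size or sign.

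Adjustment would not cure everything. Unmeasured willingness to engage would remain. So would an overlap between exposure and outcome: section 5 says "Health clinic research staff will collect uptake of testing during one of the" Open House events as well as on other clinic days, so attendance and the recorded test can be the same visit.

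**What to change.** 1. In section 7, adjust each component model and a model for the 0-3 index for pre-named baseline covariates. The core set is gender, age, HIV stigma and trust in allopathic providers. Where events allow, add immigration status, belief in the HIV test, use of traditional medicine, perceived HIV risk, and SES if recorded. Report unadjusted RRs alongside.
2. Keep the standing of the stratum-specific models, on which the study is sized, and adjust them for the core set less the stratifying variable. Take the heterogeneity p-values mentioned in section 9 from component-by-modifier terms in the adjusted model.
3. State the order in time of the components and the target of each RR. Adjust for components that come earlier. Present a joint three-component model only as supporting, because it removes any effect running through a later component. Say that single-component RRs are not free of the other components' effects.
4. In section 9, state self-selection into components, residual unmeasured confounding, and the overlap between Open House attendance and testing recorded there.

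**Cost.** This is plan wording, plus confirming that the demographics record SES and immigration status. Standard errors rise about 0 to 3% if covariates are unrelated to uptake, and roughly 5 to 20% if they are correlated with each other and with uptake (assumed correlations). The latter equals keeping 1/1.05² = 91% down to 1/1.20² = 69% of the sample's information, so the power tables would be somewhat optimistic for the adjusted analysis.

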### Calculation of Sample Size & Sampling Strategy

We anticipate approximately 5%, perhaps 10%, of study participants will test positive for HIV and not be eligible for the analysis of health facility HIV testing within 6 months among those testing **HIV negative or refusing testing**. We further estimate that 70% will complete the healer-initiated HIV test, 60% will participate in additional counseling sessions, and 50% will attend an open house. Because study participants had no history of HIV testing in the prior year, we anticipate the primary endpoint of uptake of HIV testing at the health facility will be low, approximately 30%. Finally, given the importance of identifying sub-groups which may benefit the most from the intervention components, we have powered our study to detect significant associations within strata of potential modifiers (e.g., gender). We utilized Stata psim command to conduct 500 simulations each for all combinations of the parameters described above to estimate power to detect a range of RRs.

Given our sample size of 600 study participants, with 5% testing HIV+, and for a modifying variable distributed 50%/50%, we have ~90% power to detect stratum-specific RRs of 2.0 for each intervention component (Table 1). We still retain >80% power to detect RRs of 2.25 even if uptake of HIV testing in control group is as low as 20%. Similarly, if the modifying variable is distributed 40%/60%, we retain ≥80% power to detect stratum-specific RRs of 2.0 (Table 2). Thus, the high power due to our sample size allows for robust assessment and identification of intervention associations within key subsets of participants (gender, stigma, etc.).

Given that we only anticipate 10-30 participants to test HIV+, we will be underpowered to detect a meaningful association for how the intervention components associate with uptake of ART services at the health facility within three months among those testing **HIV positive**. However, the proportion testing positive, the proportion linking to ART care, and the magnitude of the RR for the intervention components will provide important preliminary data for whether this intervention improves ART care and retention, and not just linkage to HIV prevention services (such as follow-up HIV testing in those who are negative).

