**Table 1.**

Stratum specific sample size*	Baseline uptake of health facility HIV testing	Intervention component distribution	Power for relative increase in HIV testing uptake among those with the intervention component vs. those without		
			RR=1.75	RR=2.0	RR=2.25
135	20%	40%	0.484	0.702	0.856
		50%	0.458	0.724	0.868
		60%	0.432	0.622	0.824
		70%	0.346	0.576	0.762
135	25%	40%	0.628	0.852	0.954
		50%	0.596	0.832	0.952
		60%	0.604	0.814	0.964
		70%	0.501	0.708	0.874

135	30%	40%	0.772	0.924	0.994
		50%	0.738	0.928	0.996
		60%	0.726	0.924	0.998
		70%	0.592	0.850	0.976
135	35%	40%	0.868	0.990	1.000
		50%	0.832	0.974	1.000
		60%	0.830	0.980	1.000
		70%	0.744	0.952	0.996
135	40%	40%	0.922	1.000	1.000
		50%	0.924	1.000	1.000
		60%	0.932	1.000	1.000
		70%	0.852	0.990	1.000

\*N=135 assumes ~10% test HIV+ and are excluded and the remaining participants are divided equally into two strata of a modifier (e.g., 50% female)

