**Table 2.**

Stratum specific sample size*	Baseline uptake of health facility HIV testing	Intervention component distribution	Power for relative increase in HIV testing uptake among those with the intervention component vs. those without		
			RR=1.75	RR=2.0	RR=2.25
115	20%	40%	0.464	0.660	0.814
		50%	0.412	0.596	0.802
		60%	0.346	0.536	0.770
		70%	0.298	0.468	0.654
115	25%	40%	0.574	0.780	0.928
		50%	0.546	0.782	0.932
		60%	0.536	0.746	0.898
		70%	0.412	0.624	0.820
115	30%	40%	0.646	0.896	0.974
		50%	0.676	0.902	0.986
		60%	0.638	0.852	0.958
		70%	0.516	0.796	0.934
115	35%	40%	0.796	0.972	0.998
		50%	0.802	0.972	0.998
		60%	0.716	0.958	0.998
		70%	0.638	0.910	0.994
115	40%	40%	0.908	0.992	1.000
		50%	0.914	0.996	1.000
		60%	0.858	0.990	1.000
		70%	0.794	0.986	1.000

\*N=115 assumes ~5% test HIV+ and are excluded and the remaining participants are divided unequally into two strata of a modifier (e.g., 40% female or other modifier)

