## Study Procedures

Participants will be recruited among those who present for health care services from one of our traditional healers trained in conducting HIV counseling and testing. Participants will be recruited after their healer consultation is completed to ensure we do not impact their services. Healers will screen potential participants for eligibility (no HIV test in past year, over 18 years of age, live in Agincourt) and if they are eligible, the healers will ask if they are willing to participate in a research study. Healers will state clearly that there is no obligation to participate and that choosing not to participate will in no way impact their health care from this traditional healer. Healers will consent participants via an online consent form via tablet, so all consent forms will be online and backed up to the secure Vanderbilt REDCap cloud.

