## Training Activities

To enable traditional healers to acquire the skills necessary to undertake home-based HIV testing as well as HIV coping skills counseling, traditional healers selected to participate will enroll in a 2-week course used with HIV counselors that includes certification to conduct HIV counselling and testing and basic lay counseling to develop patient coping strategies. During the testing and counseling course, 9 topics will be covered including: 1) epidemiology and pathophysiology of HIV/AIDS and disease stages, 2) attitudes and social views of HIV, an introduction to HIV counselling and testing, legal and ethical issues of HIV and HIV testing, 3) pre- and post- test counselling, 4) performing an HIV rapid test and interpretation of the results, 5) psychological stress as a result of a positive test, 6) identifying depressive symptoms (and how to refer a patient to psychological services), 7) referral and management of HIV, 8) counseling patients on primary and secondary prevention methods (including condom use, Pre-Exposure Prophylaxis [PrEP]) after HIV testing) and 9) safe disposal of HIV testing equipment. Counseling support will include the development of coping strategies to overcome the negative effects of HIV stigma, risk reduction, and linkage with appropriate community organizations.

The course content will be delivered in an iterative fashion and trainees will have ample opportunity to ask questions with facilitated discussions. Traditional healers/trainees will be asked to orally respond to questions posed by the trainer throughout the training to gauge comprehension as new concepts are introduced. More formally, both a written and practical assessment will be administered. The trainee will be required to pass to be considered proficient to undertake HIV counselling and testing. Fidelity to the intervention, including the safety of the intervention for those tested by the healers, will be monitored via monthly observation using a checklist of procedural activities. This same mechanism is currently employed with community health workers who are providing home-based HIV counseling and testing, to which we have not experienced any difficulty implementing.

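### The component risk-ratio models name no healer-level clustering, so their 95% CIs may be too narrow; separately, Tables 1 and 2 use strata that fit about 300 participants, not the stated 600

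*Combined protocol and SAP*

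**What the plan says.** **Recruitment.** Under Study Procedures (Section 5), participants are "recruited among those who present for health care services from one of our traditional healers". Recruitment and Consent (Section 8) repeats this. In both places the same healer checks eligibility, invites the patient and takes consent. Training Activities opens with the purpose of the course: "To enable traditional healers to acquire the skills necessary to undertake home-based HIV testing as well as HIV coping skills counseling".

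**Analysis.** Data Analysis (Section 7) defines four exposures: healer-initiated testing, additional counseling sessions, attendance at an Open House, and a 0–3 count of these. For the three single components it plans "separate regression models that are each further stratified by potential modifiers", using modified Poisson "models for each intervention component to estimate risk ratios and 95% confidence intervals". No section mentions clustering by healer, a cluster-robust variance, GEE, a random effect, an ICC or a design effect. Limitations (Section 9) discusses the lack of randomisation and small subgroups, but not clustering.

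**Sample size.** Section 4 says "we have powered our study to detect significant associations within strata of potential modifiers", and for Table 1 begins "Given our sample size of 600 study participants, with 5% testing HIV"-positive with a 50/50 modifier. The Table 1 footnote reads "N=135 assumes ~10% test HIV+ and are excluded and the remaining participants are divided equally into two strata". The Table 2 footnote reads "N=115 assumes ~5% test HIV+ and are excluded and the remaining participants are divided unequally into two strata".

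**The concern.** Patients of the same healer may share that healer's way of offering a test, as well as the village, the distance to a clinic and the healer's referral habits. Both the exposure (taking up a component) and the outcome (testing at a health facility) could therefore be more alike within a healer than between healers. The robust variance normally used with modified Poisson corrects the Poisson variance for a binary outcome. It allows for healer clustering only if it is clustered on healer, and the plan does not say so.

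The components differ in how plausible this is:

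- Component 1, healer-initiated testing: most plausible.
- Component 2, additional counseling: likely, but by inference. Healers are trained in counseling, yet no section says who delivers these sessions.
- Component 3, Open House at the facility: unclear.

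The component risk ratios and their intervals are the main inferential output, and Section 9 says the pilot will help develop and power a larger trial. Overstated precision could carry forward. How much it matters depends on stratum size, and on that the plan contradicts itself.

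**Working it through.** **1. The plan's own power figure.** Table 1 gives 0.928 for a stratum of 135, 30% baseline uptake, a 50% component share and RR 2.0. Assuming independent observations and two-sided 0.05 (inferred from the 95% CIs), the Wald test on the log RR has

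SE² = 0.7/(0.3 × 67.5) + 0.4/(0.6 × 67.5) = 0.0346 + 0.0099 = 0.0444, so SE = 0.211.

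Power = Φ(0.693/0.211 − 1.96) = 0.908. A two-proportion formula gives 0.947, and simulation of the robust Poisson test gives 0.938. The printed figure is thus consistent with a calculation that has no clustering term.

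**2. Stratum sizes.**

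| Rule | From 600 | From 300 | Printed |
|---|---|---|---|
| Table 1 footnote: 10% excluded, split 50/50 | 600 × 0.90 / 2 = 270 | 300 × 0.90 / 2 = 135 | 135 |
| Section 4 text for Table 1: 5% excluded, split 50/50 | 600 × 0.95 / 2 = 285 | 300 × 0.95 / 2 = 142.5 | 135 |
| Table 2 footnote: 5% excluded, 40% stratum | 600 × 0.95 × 0.40 = 228 | 300 × 0.95 × 0.40 = 114 | 115 |

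Both tables fit about 300 participants. The text also cites 5% HIV-positive for a table built on 10%.

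**3. How clustering enters.** With m participants per healer, the variance of the log RR is inflated by roughly

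DEFF = 1 + (m − 1) × ICC(uptake) × ICC(outcome).

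If either ICC is zero, DEFF is 1. At 570 participants (600 × 0.95) and 10 healers, m = 57:

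- ICCs 0.1 and 0.1: DEFF = 1 + 56 × 0.01 = 1.56, so the correct interval is √1.56 = 1.25 times as wide.
- Uptake ICC 0.1, outcome ICC 0.02: DEFF = 1 + 56 × 0.002 = 1.11, a factor of 1.05.

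**4. Simulation.** Healer numbers and ICCs are assumptions. Beta-binomial healer effects, independent between uptake and outcome; equal-sized healers; 30% outcome; 70% uptake; true RR 1; 4,000 runs per setting. Rejection by a nominal 5% test without clustering, at uptake/outcome ICCs of 0.1/0.1 and 0.2/0.1:

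| N | 10 healers | 20 healers | 30 healers |
|---|---|---|---|
| 570 | 10.7%, 16.9% | 7.9%, 10.9% | 6.6%, 9.0% |
| 270 | 7.5%, 10.4% | 5.9%, 7.6% | 5.5%, 6.3% |
| 135 | 6.0%, 6.8% | 4.3%, 5.7% | 4.9%, 5.5% |

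- Including 60% uptake as well, the ranges are 6.2–17.3% (N=570), 5.5–10.4% (270), 5.4–10.1% (228), 4.3–6.8% (135) and 4.4–6.6% (115).
- At N=570 with uptake ICC 0.1 and outcome ICC 0.02, rejection is about 4–6%. With both ICCs at 0.05 it is 4.3–6.3%. With no uptake clustering it is 3.7–5.3%.
- At RR 2.0 and outcome ICC 0.1, the nominal 95% CI covers 79.5–91.6% (N=570), 87.4–93.8% (270) and 91.4–95.0% (135).

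**5. The remedy.** With K healers, a variance clustered on healer and a t(K−1) reference rejects 3.5–5.9% over all these settings. With unequal healer sizes (CV 0.6) and 10 healers it reaches 7.3%, while a delete-one-healer jackknife with t(K−1) gives 3.0–5.7%.

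**6. What the remedy does not do.** Suppose healers who raise component uptake also raise facility testing (assumed correlation 0.5, ICCs 0.1/0.1, true RR 1, N=570). The estimated RR is then about 1.18, and the clustered t(K−1) test still rejects in about 9–16%.

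**The case against.** **The size rests on assumed inputs.** This stands. The outcome is testing at a health facility, not a service the healer delivers, so a low outcome ICC is quite possible, and at 0.02 the problem nearly vanishes. The plausible range includes no material effect.

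**The largest figures are for pooled models, while the plan stresses strata.** This stands in part. At the printed sizes of 115–135 the effect is near nil under the null. If 600 is the true total, the strata are 228–285 and the effect is intermediate.

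**Confounding is the bigger issue.** This also stands. Components are self-selected and Data Analysis names no covariate adjustment. Clustered variance does not correct a shifted estimate.

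**This is a non-randomised pilot.** True, and it lowers the stakes, but the plan still says it is powered for significant associations and will report 95% CIs.

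Two stronger readings are tempting:

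- A reader might infer that clustering destroys the stated power. The documents do not support this, because the true stratum size is unresolved. At 285 per stratum, with 15 healers and ICCs of 0.3 and 0.10, DEFF is 1 + 18 × 0.03 = 1.54 and power for RR 2.0 is still about 0.99. Only if strata really are 135 does a clustered test fall short: 0.72–0.86 with 15 healers over the assumed ICCs 0.1/0.05 to 0.3/0.10, against 0.90 for the same test with no clustering present.
- A reader might infer that the heterogeneity tests in Section 9 are invalid. When healer effects are shared across subgroups, those tests reject 3.9–5.5% without clustering, or up to 6.0% if the modifier itself clusters by healer (ICC 0.1).

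**Conclusion.** The point holds as a conditional one. Participants are grouped by healer and the plan's intervals do not allow for it. The intervals are too narrow only if uptake and facility testing both vary by healer. With 10–30 healers assumed, the error rate of a nominal 5% test at N=570 runs from about 4–6% at a low outcome ICC to about 7–17% at an outcome ICC of 0.1. It is up to about 10% at 228–270 and close to nominal at 115–135. The documents cannot narrow this range. Naming the clustering is a cheap improvement to the plan, not the repair of a demonstrated error. It corrects precision only, so the component RRs remain associations.

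The sample-size mismatch rests on no assumption and is wrong as written: 600 participants cannot give strata of 135 and 115 under the stated rules, and the 5% in the text conflicts with the 10% under Table 1.

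**What to change.** **Data Analysis (Section 7).** Keep the same models. State that the variance is clustered on the recruiting healer, with a t reference on the number of healers minus one. If there are only about 10 healers, or their numbers of participants are very unequal, use a delete-one-healer jackknife variance with the same reference. Add that this does not remove confounding by healer and that the component RRs are read as associations.

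**Data Management (Section 7).** State that the recruiting healer's ID is linked to each participant's coded number. The documents do not say whether it is, and it may be hard to recover after enrolment.

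**Sample size (Section 4, Tables 1 and 2).** Reconcile 600 with strata of 135 and 115, and 5% with 10% HIV-positive. Then restate the power figures for the true total.

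**Cost.** A few sentences, one ID link if it is not already held, and a rerun of the power tables. If uptake does not cluster by healer, intervals on the log RR scale are about 3–12% wider with t(K−1), or 4–20% with the jackknife, for no gain. Under the assumed ICCs of 0.1–0.2 for uptake and 0.1 for outcome, pooled intervals widen by about 11–48% with t(K−1); there the extra width is the correction itself.
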